9.8 Analysis of Safety

The safety outcomes of this study include the frequency of adverse events (AE) and severe adverse events (as defined in section 10.0). Descriptive statistics will be presented, including the number and percentage of subjects with any AE.

Summaries will be prepared for all treatment emergent AEs, including:

- Study-drug-related AEs
- AEs that are Grade 3, 4, or 5 in severity
- AEs leading to dose modification
- AEs leading to study drug discontinuation
- SAEs

Safety analyses will be performed for all patients having received at least one dose of study treatment. The proportion of subjects experiencing adverse events, serious adverse events, and treatment delays will be summarized. Tolerability will be assessed based on dosage delays and discontinuation due to adverse events.

All AEs will be listed, documenting the course, outcome, severity, and relationship to the study treatment. Incidence rates of AEs and the proportion of subjects prematurely withdrawn from the study due to AEs will be shown.

9.9 Handling of Dropouts and Missing Data

No data imputation will be performed.

10.0 Adverse Event Reporting

The investigator will monitor each subject for clinical and laboratory evidence of adverse events on a routine basis throughout the study. The investigator will assess and record any adverse event in detail, including the date of onset, event diagnosis (if know) or sign/symptom, severity, time course (end date, ongoing, intermittent), relationship of the adverse event to study drug, and any action(s) taken.

An adverse event (AE) is defined as any untoward medical occurrence in a patient or clinical investigation subject administered a pharmaceutical product and which does not necessarily have a causal relationship with this treatment. A treatment-emergent adverse event is defined as any AE reported by a subject with onset or worsening from the time that the first dose of HDMP + Rituximab is administered until 30 days have elapsed following the discontinuation of study drug administration.

The severity of non-hematologic adverse events will be rated according to National Cancer Institute Common Terminology Criteria for Adverse Events (NCI CTCAE Version 4.0).

The severity of hematologic adverse events will be rated according to 2008 iwCLL grade scale. As is the case with virtually all of the hematological malignancies, an evaluation of the hematological toxicity in patients with CLL must consider the high frequency of marrow involvement and consequent medullar compromise at the initiation of therapy. A substantial proportion of patients will have hematological parameters within the range of Grade 2-4 hematological toxicity before therapy is given; therefore, a modified schema will be used to monitor hematological toxicity in patients with CLL. The modified hematological toxicity schema (taken directly from Hallek et al, 2008 IWCLL criteria) is displayed:

Grading scale for hematologic toxicity in CLL studies

Grade	Decrease in platelets [†] or Hb [‡] (nadir) from pretreatment value, %	Absolute neutrophil count/ µL [§] (nadir)
0	No change to 10%	≥ 2000
1	11%-24%	≥ 1500 and < 2000
2	25%-49%	≥ 1000 and < 1500
3	50%-74%	≥ 500 and < 1000
4	≥ 75%	< 500

- → Grades: 1, mild; 2, moderate; 3, severe; 4, life-threatening; 5, fatal. Death occurring as a result of toxicity at any level of decrease from pretreatment will be recorded as grade 5.
- $_{-}$ † Platelet counts must be below normal levels for grades 1 to 4. If, at any level of decrease, the platelet count is < 20×10^9 /L ($20\,000/\mu$ L), this will be considered grade 4 toxicity, unless a severe or life-threatening decrease in the initial platelet count (eg, 20×10^9 /L [$20\,000/\mu$ L]) was present pretreatment, in which case the patient is not evaluable for toxicity referable to platelet counts.
- → ‡ Hb levels must be below normal levels for grades 1 to 4. Baseline and subsequent Hb determinations must be performed before any given transfusions. The use of erythropoietin is irrelevant for the grading of toxicity but should be documented.
- \downarrow § If the absolute neutrophil count (ANC) reaches < 1 × 10⁹/L (1000/µL), it should be judged to be grade 3 toxicity. Other decreases in the white blood cell count, or in circulating neutrophils, are not to be considered because a decrease in the white blood cell count is a desired therapeutic endpoint. A gradual decrease in granulocytes is not a reliable index in CLL for stepwise grading of toxicity. If the ANC was < 1 × 10⁹/L (1000/µL) before therapy, the patient is not evaluable for toxicity referable to the ANC. The use of growth factors such as G-CSF is not relevant to the grading of toxicity, but should be documented.

If the reported AE increases in severity, the initial adverse events should be given final outcome date and a new adverse event must be reported to reflect the change in severity.

SAE definition:

An AE should be classified as an SAE if the following criteria are met:

- It results in death (i.e., the AE actually causes or leads to death)
- It is life threatening (i.e., the AE, in the view of the investigator, places the patient at immediate
 risk of death. It does not include an AE that, had it occurred in a more severe form, might have
 caused death).

- It requires or prolongs inpatient hospitalization
- It results in persistent or significant disability/incapacity (i.e., the AE results in substantial disruption of the patient's ability to conduct normal life functions)
- It results in a congenital anomaly/birth defect in a neonate/infant born to a mother exposed to the IMP
- It is considered a significant medical event by the investigator based on medical judgment (e.g., may jeopardize the patient or may require medical/surgical intervention to prevent one of the outcomes listed above)

SAE Reporting:

Events meeting the following criteria need to be submitted to the FDA as expedited IND Safety Reports according to the following guidance and timelines:

7 Calendar Day Telephone or Fax Report

The Investigator is required to notify the FDA of any fatal or life-threatening AE that is unexpected and assessed by the investigator to be possibly related to the use of HDMP, Rituximab, and venetoclax. An unexpected AE is one that is not already described in the venetoclax investigator brochure or the methylprednisolone and rituximab prescribing information. Such reports are to be telephoned or faxed to the FDA within 7 calendar days of first learning of the event.

15 Calendar Day Written Report

The Investigator is also required to notify the FDA and all participating investigators, in a written IND Safety Report, of any serious, unexpected AE that is considered reasonably or possibly related to the use of HDMP, rituximab, or venetoclax. An unexpected AE is one that is not already described in the venetoclax investigator brochure or the methylprednisolone and rituximab prescribing information.

Written IND Safety reports should include an Analysis of Similar Events in accordance with regulation 21 CFR § 312.32. All safety reports previously filed by the investigator with the IND concerning similar events should be analyzed and the significance of the new report in light of the previous, similar reports commented on.

Written IND safety reports with analysis of similar events are to be submitted to the FDA, Abbvie, and all participating investigators within 15 calendar days of first learning of the event. MedWatch 3500 form or alternative formats will be used (e.g., summary letter).

Contact Information for IND Safety Reports

FDA fax number for IND safety reports:

Fax: [name]

In addition to compliance with all FDA reporting requirements pursuant to 21 CFR 312, the Principal Investigator shall:

- d) Report to Abbvie all serious adverse events experienced by a study subject receiving an AbbVie product within 24 hours of learning of the event regardless of the relationship of the event to the AbbVie product. Principal Investigator shall make available to AbbVie promptly such records as may be necessary and pertinent to investigate any such event, if specifically requested by AbbVie; and in addition, report all non-serious adverse events of tumor lysis syndrome for studies involving ABT-199.
- e) Copy AbbVie on the submission to the FDA of events meeting the definition of IND safety reports at the time of submission to the Agency; and,
- f) Notify AbbVie upon any subjects receiving an AbbVie Product whose pregnancy has resulted in a negative outcome or untoward event during the course of pregnancy or upon delivery.

AbbVie's contact for reporting serious adverse drug experiences, pregnancy experiences, non-serious adverse events of tumor lysis syndrome, and communication of FDA submissions of IND safety reports shall be [contact]

Product Complaints: In addition to compliance with all FDA requirements pursuant to 21 CFR 211 and 21 CFR 820, Principal Investigator will report to AbbVie within 24 hours any suspected quality defect in an AbbVie Product or its AbbVie-provided packaging, labeling, or medical device component (collectively, "Product Complaint"). Principal Investigator will report Product Complaints that involve an AbbVie Product, whether AbbVie has supplied the AbbVie Product used in the Study or not. AbbVie's contact for reporting Product Complaints shall be RD PQC [contact]

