6.6 End of Study Assessment

Within 2 weeks before or after Cycle 24, Day 28, the following are completed:

- History and physical examination including vital signs.
- Current medications will be recorded in the subject's medical record.
- Laboratory examinations: CBC w/differential, comprehensive metabolic panel.
- Collection of correlative sample.
- CT or MRI of thorax, abdomen, and pelvis.
- Marrow biopsy and aspirate if clinical examination is consistent with a complete remission (ie, absolute lymphocyte count less than 4k/uL) and if clinically indicated to determine subsequent therapy (e.g.: stopping therapy if undetectable minimal residual disease).

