6.7 Long-term follow-up

No long-term follow-up visits are scheduled or required per study.

With patient consent, date of progression or next CLL therapy will be recorded based on chart review if data are available, or phone call no more than every 6 months.

6.8 Subject Withdrawal or Treatment Discontinuation:

Patients who meet or develop the following criteria should be discontinued from the study

- Active HBV infection or hepatitis. Patients who are carriers of hepatitis B at the time of discontinuation from study treatment will continue to be followed for clinical and laboratory signs of active HBV infection and for signs of hepatitis.
- Severe or life-threatening anaphylaxis or hypersensitivity reaction to rituximab. Patients that discontinue rituximab for that reason can continue to receive HDMP and venetoclax if clinically indicated.
- Patients who meet the following criteria should discontinue HDMP: Grade 4 psychosis; Active HBV infection or hepatitis as above. HDMP doses can be delayed for acute infection or as clinically indicated.
- Inability of patient to comply with study requirements
- Determination by the investigator that it is no longer safe for the patient to continue therapy

With the exception of following HBV, patients who withdraw from all study therapy do not have required follow-up visits and can enter long-term follow-up (6.7). With patient consent, date of progression or next CLL therapy will be recorded.

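### Treatment-emergent events are counted to 30 days after study drug stops, but no required contact covers the end of that window, so late events may be under-ascertained

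*Combined protocol and SAP*

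**What the plan says.** Section 10.0 starts the treatment-emergent window at the first dose of HDMP plus rituximab and keeps it open "until 30 days have elapsed following the discontinuation of study drug administration". Section 9.8 summarises treatment-emergent AEs by relatedness, severity, seriousness and effect on dosing, and plans a listing that shows the course and outcome of every AE.

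The visit schedule stops earlier. Section 6.6 sets the last visit: "Within 2 weeks before or after Cycle 24, Day 28, the following are completed". Table 3 agrees. Section 6.7 then states: "No long-term follow-up visits are scheduled or required per study". What it does collect, with the patient's consent, is limited: "date of progression or next CLL therapy will be recorded based on chart review if data are available". The alternative to chart review is a telephone contact, at most once in any 6 months. Adverse events are not named there.

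For early stopping, section 6.8 says that, apart from following hepatitis B, "patients who withdraw from all study therapy do not have required follow-up visits and can enter long-term follow-up (6.7". The exception is that hepatitis B carriers "will continue to be followed for clinical and laboratory signs of active HBV infection".

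Section 10.0 also has a general surveillance statement: "The investigator will monitor each subject for clinical and laboratory evidence of adverse events on a routine basis throughout the study". It names no contact after the last dose.

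**The concern.** The plan defines a window for counting events but does not schedule the observation needed to fill it. A site could follow sections 6.6 to 6.8 exactly and have no occasion to ask about an infection, cytopenia or death in the weeks after the last dose. Section 9.9 allows no imputation, so an event nobody learns of is in effect counted as no event.

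Safety by CTCAE is a secondary objective (section 3.0), and the annual report to the DSMB includes a summary of all adverse events (section 11.2). Events after the last dose are plausible on the protocol's own account: section 7.2.3 warns of serious infections during and after rituximab-based therapy. At stake are the number of late events, the recorded outcome of events still open at the last visit, and the percentage of subjects with an event when the late one is their first.

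**Working it through.** The plan states no figure on this point, so the check is calendar arithmetic on the stated windows.

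**Inputs**
- Window after last dose: 30 days (section 10.0).
- Last visit: Cycle 24 Day 28, from -14 to +14 days (section 6.6, Table 3).
- Required visits after withdrawal from all therapy: none, hepatitis B follow-up excepted (section 6.8).
- Last venetoclax cycle: 24 (section 6.5) or 26 (synopsis, study procedures).
- Supply dispensed on Day 1 of Cycle 22: 90 days (section 6.5); three cycles are 3 x 28 = 84 days.
- Planned sample size: 17 (section 9.2).

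**Uncovered post-dose days** = 30 - max(0, visit day - last-dose day).

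| Last dose | Visit at -14 | Visit at 0 | Visit at +14 |
|---|---|---|---|
| Cycle 24 Day 28 | 30 | 30 | 30 - 14 = 16 |
| 6 days later (90-day supply finished) | 30 | 30 | 30 - (14 - 6) = 22 |
| Cycle 26 Day 28 (2 x 28 = 56 days later) | 30 | 30 | 30 |
| Early withdrawal from all therapy | up to 30 | up to 30 | up to 30 |

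With the last dose on Cycle 24 Day 28, a visit at -14 also leaves the last 14 treatment days unobserved. With the last dose on Cycle 26 Day 28, the visit falls 56 - 14 = 42 to 56 + 14 = 70 days before that dose.

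**Effect of one missed SAE.** 1/17 = 5.9 percentage points on the percentage of subjects with an SAE, if that patient had no earlier SAE. Otherwise the percentage does not move, and only the listing and the event count are incomplete.

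**Who holds the uncovered time.** Let f be the fraction stopping all therapy for toxicity, each with 30 uncovered days. Assume all others complete with u uncovered days each, u = 16 to 30. The toxicity stoppers' share of uncovered person-days is 30f / (30f + u(1 - f)). The documents give no f for this regimen. The 8.3% in section 7.3.3 sits among pooled single-agent data, so it serves here only as an illustrative assumption.

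- f = 8.3% (0.083 x 17 = 1.4 patients): 2.49 / (2.49 + 14.67) = 14.5% at u = 16; 8.3% at u = 30.
- f = 20%: 6 / (6 + 12.8) = 32% at u = 16; 20% at u = 30.
- f = 30%: 9 / (9 + 11.2) = 45% at u = 16; 30% at u = 30.

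The share passes one half only if f exceeds 16/46 = 35% (u = 16) or 50% (u = 30). At f = 8.3%, toxicity stoppers would account for most missed events only if their event rate per uncovered day were more than 14.67/2.49 = 5.9 times (u = 16) to 27.51/2.49 = 11.0 times (u = 30) that of completers.

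**The case against.** The best reply is that the plan has other routes by which late events come to light. Section 10.0 calls for routine monitoring throughout the study. SAEs go to the drug supplier within 24 hours of the investigator learning of them, with no end date. Section 6.7 permits chart review, and this is a single-center trial. Section 8.3 moves the marrow assessment forward if treatment stops early, and section 8.4 names an end-of-treatment visit. The waiver of visits covers only withdrawal from all therapy: a patient who stops rituximab for hypersensitivity can continue on the other drugs (section 6.8), and one who cannot tolerate 20 mg of venetoclax may stay on study (Table 5).

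This shows that late events are not necessarily lost; any that are learned of within the window still count. It does not close the gap. The 24-hour duty is passive, hepatitis B follow-up covers only that condition, the end-of-treatment visit is a blood draw with no day set relative to the last dose, the marrow serves MRD, and staying on study after venetoclax intolerance is for progression.

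The second reply concerns consequence, and it largely stands. Section 9.8 counts subjects with events, and a patient who stopped for toxicity already has at least one AE. Section 7.3.3 quotes serious adverse reactions in 46% of patients on venetoclax with rituximab, so the condition of no earlier SAE would often fail. Safety is descriptive and outside the sample-size calculation (section 9.2).

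**Conclusion.** The gap is real. The window runs to day 30, but no required contact covers its end: 16 to 30 post-dose days are unobserved for completers with a last dose on Cycle 24 Day 28, and up to 30 for those who withdraw from all therapy. Late events and outcomes may be under-ascertained. The primary endpoint is assessed before venetoclax, and the TLS endpoints close with the ramp-up, so neither depends on contact after the last dose. Alpha and power do not change.

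A reader might infer that the missed events fall mostly in patients who stopped for toxicity. Those patients may plausibly have more events per day, but the documents give no such rate, and completers also lack 16 to 30 days each. Unless toxicity stops are far commoner than the illustrative 8.3%, completers hold most of the uncovered time. Nor do the documents support saying that early stoppers have no contact whatever, that late events are certain to go uncounted, or that every missed SAE shifts the rate by 5.9 points.

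The completer figures rest on which cycle is the last, and the documents conflict on that. This is worth correcting because the remedy is cheap, not because it threatens the trial's main conclusion.

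**What to change.** In sections 6.6, 6.7 and 6.8, and as a line in Table 3, require one safety contact by telephone or chart review at 30 days (for example +7 days) after the last dose of all study drug. Apply it to completers and to everyone who stops early. It should record new AEs, SAEs and the outcome of AEs still open. Section 6.7 already permits both channels; its content must be widened beyond progression and next therapy, and its limit on call frequency must not block this call. A contact on or after day 30 reduces the uncovered days to zero for every patient reached.

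Reconcile the 24-cycle end of treatment (sections 6.5 and 6.6) with the 26-cycle end in the synopsis, so that the date from which the 30 days run is unambiguous.

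The cost is a short amendment and about 17 calls or chart checks. Reported AE rates may rise slightly. Treatment, sample size and the primary analysis are unchanged.

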7.1.3 Adverse Reactions

Adverse Reactions Significant (Frequency not defined).

Cardiovascular: Arrhythmias, bradycardia, cardiac arrest, cardiomegaly, circulatory collapse, congestive heart failure, edema, fat embolism, hypertension, hypertrophic cardiomyopathy in premature infants, myocardial rupture (post MI), syncope, tachycardia, thromboembolism, vasculitis

Central nervous system: Delirium, depression, emotional instability, euphoria, hallucinations, headache, intracranial pressure increased, insomnia, malaise, mood swings, nervousness, neuritis, personality changes, psychic disorders, pseudotumor cerebri (usually following discontinuation), seizure, vertigo

Dermatologic: Acne, allergic dermatitis, alopecia, dry scaly skin, ecchymoses, edema, erythema, hirsutism, hyper-/hypopigmentation, hypertrichosis, impaired wound healing, petechiae, rash, skin atrophy, sterile abscess, skin test reaction impaired, striae, urticarial

Endocrine & metabolic: Adrenal suppression, amenorrhea, carbohydrate intolerance increased, Cushing's syndrome, diabetes mellitus, fluid retention, glucose intolerance, growth suppression (children), hyperglycemia, hyperlipidemia, hypokalemia, hypokalemic alkalosis, menstrual irregularities, negative nitrogen balance, pituitary-adrenal axis suppression, protein catabolism, sodium and water retention.

Gastrointestinal: Abdominal distention, appetite increased, bowel/bladder dysfunction (after intrathecal administration), gastrointestinal hemorrhage, gastrointestinal perforation, nausea,

pancreatitis, peptic ulcer, perforation of the small and large intestine, ulcerative esophagitis, vomiting, weight gain.

Hematologic: Leukocytosis (transient).

Hepatic: Hepatomegaly, transaminases increased.

Local: Thrombophlebitis.

Neuromuscular & skeletal: Arthralgia, arthropathy, aseptic necrosis (femoral and humoral heads), fractures, muscle mass loss, muscle weakness, myopathy (particularly in conjunction with neuromuscular disease or neuromuscular-blocking agents), neuropathy, osteoporosis, parasthesia, tendon rupture, vertebral compression fractures, weakness.

Ocular: Cataracts, exophthalmoses, glaucoma, intraocular pressure increased.

Renal: Glycosuria.

Respiratory: Pulmonary edema.

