7.3.3 Adverse Reactions and Precautions

The safety of single agent VENCLEXTA at the 400 mg recommended daily dose following a dose ramp-up schedule is based on pooled data of 240 patients with previously treated CLL from two phase 2 trials and one phase 1 trial. In the pooled dataset, the median age was 66 years (range: 29 to 85 years), 95% were white, and 69% were male. The median number of prior therapies was 3 (range: 1 to 12). The median duration of treatment with VENCLEXTA at the time of data analysis was approximately 10.3 months (range: 0 to 34.1 months). Approximately 46% of patients received VENCLEXTA for more than 48 weeks.

The most common adverse reactions (≥20%) of any grade were neutropenia, diarrhea, nausea, anemia, upper respiratory tract infection, thrombocytopenia, and fatigue.

Serious adverse reactions were reported in 43.8% of patients. The most frequent serious adverse reactions (≥2%) were pneumonia, febrile neutropenia, pyrexia, autoimmune hemolytic anemia (AIHA), anemia, and TLS.

In combination with rituximab, serious adverse reactions were reported in 46% of patients, with the most frequent (\geq 5%) being pneumonia (9%). The most common adverse reactions (\geq 20%) of any grade were neutropenia (65%), diarrhea (40%), upper respiratory tract infection (39%), fatigue (22%), cough (22%), and nausea (21%).

Discontinuations due to adverse reactions occurred in 8.3% of patients. The most frequent adverse reactions leading to drug discontinuation were thrombocytopenia and AIHA.

Dosage adjustments due to adverse reactions occurred in 9.6% of patients. The most frequent adverse reactions leading to dose adjustments were neutropenia, febrile neutropenia, and thrombocytopenia.

Specific warnings and precautions:

Tumor Lysis Syndrome

Tumor lysis syndrome, including fatal events and renal failure requiring dialysis, has occurred in previously treated CLL patients with high tumor burden when treated with VENCLEXTA.

VENCLEXTA can cause rapid reduction in tumor and thus poses a risk for TLS in the initial 5-week ramp-up phase. Changes in blood chemistries consistent with TLS that require prompt management can occur as early as 6 to 8 hours following the first dose of VENCLEXTA and at each dose increase.

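### The 7-day FDA rule asks for relatedness to all three drugs where the 15-day rule asks for any one, and both rules test expectedness against one pooled list, so a venetoclax-only event can count as expected because another drug's label lists it

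*Combined protocol and SAP*

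**What the plan says.** Section 10.0 (Adverse Event Reporting) sets two expedited FDA reports. The same wording stands in item 10.0 of the synopsis table.

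- **7-day report.** It covers fatal or life-threatening events that are unexpected and judged "possibly related to the use of HDMP, Rituximab, and venetoclax".
- **15-day report.** It covers serious, unexpected events "considered reasonably or possibly related to the use of HDMP, rituximab, or venetoclax".
- **Expectedness.** Both rules use one sentence: "An unexpected AE is one that is not already described in the venetoclax investigator brochure or the methylprednisolone and rituximab prescribing information". It therefore appears four times, twice in Section 10.0 and twice in the synopsis.
- **Attribution.** For each adverse event, Section 10.0 asks the investigator to record the "relationship of the adverse event to study drug, and any action(s) taken". Section 9.8 says "All AEs will be listed, documenting the course, outcome, severity, and relationship to the study treatment". Neither asks for a separate judgement on each drug.

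Section 10.0 also places its supplier-reporting duties on top of compliance with 21 CFR 312. It sends serious events in subjects receiving the supplier's product to the venetoclax supplier within 24 hours, whatever their relationship to it.

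**The concern.** The two rules stand next to each other but use different relatedness tests, and the stricter wording is attached to the more urgent report. Staff who follow the 7-day text literally would hold back the fast report of a death attributed to a single drug.

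The pooled expectedness sentence has a different effect. It can remove an event from both reports, because each requires the event to be unexpected. The event at risk is a serious one blamed on venetoclax, new for venetoclax, but already known for the steroid or the antibody. The steroid is scheduled on three days of Cycle 0, yet its label can make a venetoclax event expected many months later.

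**Working it through.** The plan gives no figure to reproduce. The check follows the rules as written. The counts below are counts of logical patterns, not probabilities.

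**Relatedness (Section 10.0, both rules)**

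1. With three drugs, the possible sets of suspected drugs number 2^3 − 1 = 7.
2. The 15-day *or* is met by all 7.
3. The 7-day *and*, read strictly, is met by 1 (all three drugs suspected).
4. Cycle 0 contains only methylprednisolone and rituximab (Section 6.2), and venetoclax starts on Day 1 of Cycle 1 (Section 6.3). An event before that day cannot be related to all three drugs, so on the strict reading it can never meet the 7-day rule.
5. Death and threat to life are both seriousness criteria in Section 10.0. Such an event, if unexpected, still meets the 15-day rule. The loss is in timing only: 15 − 7 = 8 days at most.

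**Expectedness (Section 10.0, sentence shared by both rules)**

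Take a serious event attributed only to venetoclax and absent from the venetoclax brochure. The other two labels give 2^2 = 4 listing patterns.

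| Methylprednisolone label | Rituximab label | Natural reading (either label suffices) | If both labels must list it | Suspected drug's own document |
|---|---|---|---|---|
| no | no | unexpected | unexpected | unexpected |
| yes | no | expected | unexpected | unexpected |
| no | yes | expected | unexpected | unexpected |
| yes | yes | expected | expected | unexpected |

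The event is called expected in 3 of 4 patterns on the natural reading and in 1 of 4 on the narrower one. Tested against the suspected drug's own document, it is unexpected in 4 of 4.

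**Is venetoclax-only attribution plausible?**

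In the body text, with one Cycle 0, scheduled time is 28 + 35 + 5 × 28 + 18 × 28 = 707 days (Sections 6.2 to 6.5). Venetoclax is the only study drug scheduled in Cycle 1 and Cycles 7 to 24: 35 + 504 = 539 days, or 539/707 = 76%. Lingering rituximab effects may still be suspected in part of that time.

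**Illustration, resting on an assumption**

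Section 7.1.3 lists "pancreatitis, peptic ulcer, perforation of the small and large intestine" for methylprednisolone. Section 7.3.3 names none of these for venetoclax. If the brochure is also silent, pancreatitis needing hospital admission in Cycle 12 and attributed to venetoclax alone would count as expected. The brochure is not among the documents, so its silence is assumed.

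**The case against.** **The plan follows the regulation anyway.** Section 10.0 invokes 21 CFR 312 and Section 11.4 invokes Title 21, and a protocol may take in a regulation by reference. This stands as a limit on the harm: an event *can* miss the report, and the documents do not show that it *will*. But neither clause states another expectedness test, while the protocol gives staff an explicit one.

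**Other routes exist.** The 24-hour supplier report does not depend on relationship or expectedness, and the DSMB receives all adverse events yearly (Section 11.2). This also stands. However, neither is an FDA report, and the supplier clause is worded for subjects receiving its product, so its reach before the first venetoclax dose is unclear.

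**The *and* is loose drafting.** Probably so, since a strict reading would bar every Cycle 0 event before venetoclax. That explains the word but does not make the two adjacent rules agree.

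**The expectedness sentence may pair each drug with its own document.** On that reading the gap closes. Nothing in the text limits the test to the suspected drug, so the reading is possible but not stated.

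**Regimen-level rules suit a combined strategy.** A reader might infer that the present 15-day trigger already depends on per-drug attribution that the plan fails to collect. The documents do not support this: an *or* trigger needs only relatedness to some part of the regimen, which Sections 9.8 and 10.0 do record. Per-drug attribution is needed for the corrected test, not for the current one.

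A reader might also try to count lost reports from the serious-reaction rates in Section 7.3.3. Those rates come from regimens without high-dose methylprednisolone, and they count reactions, not events whose listing status differs between drugs. They do not measure missed reports.

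**Conclusion.** Both defects are in the text, in Section 10.0 and in the synopsis. The *and* in the 7-day rule costs up to 8 days on a literal reading. The pooled list can remove a venetoclax-only event from expedited reporting altogether, in 3 of 4 listing patterns or 1 of 4 according to how the sentence is read.

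The number of affected events cannot be worked out from the documents. The conclusion assumes that staff apply the stated sentences as written, and any named example assumes that the brochure does not list the event. No endpoint or analysis changes. Severity: minor.

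**What to change.** 1. In the 7-day rule, in Section 10.0 and the synopsis, change *and* to *or* between the drugs.
2. In all four places, replace the expectedness sentence with: *An AE is unexpected if it is not described in the reference document of the drug to which the investigator considers it related: the investigator brochure for venetoclax, the prescribing information for methylprednisolone and for rituximab.*
3. Because the new test needs it, add to Section 10.0: *For each SAE, the investigator records the relationship to methylprednisolone, to rituximab and to venetoclax separately.*

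The sponsor should also say how an event attributed to more than one drug is handled. The cautious choice is to call it unexpected if any suspected drug's document omits it. The documents do not require this. It would bring in some known rituximab or steroid reactions co-attributed to venetoclax, for rituximab most likely in Cycles 2 to 6, when the two are given together.

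The cost is one word in two places, one sentence in four, and two more attribution entries per serious event (three instead of one, if the case report form, which is not in the documents, now has one). A few extra expedited reports may follow.
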